## **7.0 SUPPORTIVE CARE AND OTHER CONCOMITANT THERAPY**

### **7.1 Concurrent Anti Lymphatic Malformation Therapy**

Concurrent lymphatic malformation therapy, including surgery, immunotherapy, or biologic therapy may NOT be administered to patients receiving study drug >4 weeks prior to study initiation and during the study period. If these treatments are administered the patient will be removed from protocol therapy.

### **7.2 Investigational Agents**

No other investigational agents may be given while the patient is on study.

### **7.3 Supportive Care**

Patients with lymphedema should continue to receive appropriate supportive care, including compression garments, massage, and protective skin care dressings/preparations (emollients or barrier agents that protect involved skin).

### **7.4 Concomitant Medications**

Patients who require treatment with oral antibiotics for minor soft tissue infections may continue to receive these during the study. Antibiotics prescribed to be determined by infectious disease specialist, based on the patient's particular past history of infections and potential involved flora. If the patient is determined to need hospital admission for IV antibiotics, the patient will be removed from the study.

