## **10.0 CRITERIA FOR REMOVAL FROM PROTOCOL THERAPY AND OFF STUDY CRITERIA**

10.1 **Criteria for Removal from Protocol Therapy**

- Intercurrent illness that prevents further administration of treatment.
- Adverse Events requiring removal from study (See Section 6.0).
- Refusal of further protocol therapy by patient/parent/guardian

- d) Non-compliance that in the opinion of the investigator does not allow for ongoing participation.
- e) Completion of 2 months of therapy.
- f) Physician determines it is not in the patient's best interest.

Patients who are off protocol therapy are to be followed until they meet the criteria for Off Study (see below). Ongoing adverse events, or adverse events that emerge after the patient is removed from protocol therapy, but within 30 days of the last dose of investigational agent, must be followed until resolution or stabilization of the adverse event. Follow-up data will be required unless consent is withdrawn.

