## 10.2 Off Study Criteria

- a) Completion of 10 months of follow-up after the last dose of the investigational agent.
- b) Death
- c) Lost to follow-up
- d) Withdrawal of consent for any further data submission
- e) Enrollment onto another anti-lymphatic malformation study

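### Section 7.4 takes a patient admitted for IV antibiotics off the study rather than off therapy; read literally, this can lose the only post-baseline MRI, QMR and body-water values

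*Combined protocol and SAP*

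**What the plan says.** Section 7.4 allows oral antibiotics for minor soft-tissue infection during the study and then sets a rule for the serious case: "If the patient is determined to need hospital admission for IV antibiotics, the patient will be removed from the study". Section 7.1, in the same chapter, deals with prohibited concurrent treatment differently: "If these treatments are administered the patient will be removed from protocol therapy".

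Section 10 treats stopping drug and leaving the study as separate states. Among the reasons in 10.1 for stopping protocol therapy are "Intercurrent illness that prevents further administration of treatment" and "Physician determines it is not in the patient's best interest". For patients who have stopped, 10.1 states: "Follow-up data will be required unless consent is withdrawn". Section 10.2 has five off-study reasons: "Completion of 10 months of follow-up after the last dose of the investigational agent", death, loss to follow-up, withdrawal of consent to further data, and entry to another trial in lymphatic malformation. Admission and IV antibiotics are not among them.

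Table 6 marks questionnaires and lesion measurements at six time points (pre-study and Weeks 1, 2, 4, 6 and 8). It marks MRI, QMR and body-water evaluation at two (pre-study and Week 8). It has no column for early termination or for patients off therapy. Section 12.4 repeats the MRI at 8 weeks. Section 11.5 puts every eligible patient who received propranolol in the main response analysis.

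**The concern.** If 7.4 means what it says, a patient admitted for IV antibiotics before Week 8 leaves the study and nothing more is collected. Interim questionnaires and girth measurements would survive. MRI, QMR and body water would not, because Week 8 is their only post-baseline time point.

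The reason for the loss is unlikely to be neutral. Section 2.1 describes severe infection as part of this disease and counts fewer infections among the improvements seen in the retrospective series. The Abstract says that infections temporarily overcame the drug's effect at the lower doses. Patients lost in this way may be those with worse disease or a weaker response. A before-after summary of imaging and body water restricted to patients with Week 8 data could then look somewhat better than one covering everyone treated. This is plausible; the documents do not show it.

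**Working it through.** **1. Is the admission an off-study event?** The relevant texts side by side:

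| Place | What happens to the patient |
|---|---|
| 7.4 | Admission for IV antibiotics: out of the study, no return mentioned |
| 7.1 | Prohibited treatment given: off protocol therapy |
| 10.1 | Intercurrent illness, or physician's judgement: off protocol therapy, still followed, data still required |
| 10.2 | Five off-study reasons; this admission is not one |

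Taken literally, 7.4 adds an off-study reason that 10.2 does not have. Taken as a reason to stop drug, it fits under 10.1.

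**2. Would reading 7.4 as stopping drug secure the Week 8 data?** Not explicitly. Section 10.1 requires follow-up data without saying which. Table 6 has no off-therapy column. Section 12.4 times the MRI at 8 weeks and section 2.4 refers to the study endpoint, but neither addresses patients who have stopped early. Sections 8.4 and 12.4.1 describe who is assessed for response, but not what to do when Week 8 imaging is missing.

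**3. What one removal costs that patient.** Take removal just after the Week 4 visit. Questionnaires and lesion measurements have been obtained at pre-study and Weeks 1, 2 and 4, so 4 of 6. MRI, QMR and body water have been obtained once, so 1 of 2 and no change value.

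**4. What one removal costs the analysis.** Section 11.1 plans 15 to 20 patients. Its accrual rate gives 8 × 2 = 16 to 10 × 2 = 20 over 24 months, consistent with that range.

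- Share of the 11.5 set without post-baseline imaging: 1/20 = 5.0% to 1/15 = 6.7%.
- The standard error of a mean change scales as 1/√n for a fixed standard deviation: √(20/19) = 1.026 and √(15/14) = 1.035, a rise of 2.6% to 3.5%.
- The completers' mean differs from the full-set mean by d/n, that is d/20 to d/15, where d is the difference between the removed patient's change and the completers' mean change. The documents give no value for d.

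**5. Primary aim 1.1.1 (QMR against dilution).** Each patient contributes a pair of measurements at pre-study and another at Week 8: 2 × 20 = 40 or 2 × 15 = 30 pairs. One lost pair is 1/40 = 2.5% or 1/30 = 3.3%. The standard error rises by at most √(40/39) = 1.013 or √(30/29) = 1.017, treating pairs as independent. It rises less if a patient's two pairs are correlated. The baseline pair is kept.

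**6. How likely is a loss?** The documents give no admission rate. The rates below are assumptions; the chance of at least one loss is 1 − (1 − p)^n.

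| Assumed rate before Week 8 | 15 patients: expected, chance of ≥1 | 20 patients: expected, chance of ≥1 |
|---|---|---|
| 5% | 0.75, 53.7% | 1, 64.2% |
| 10% | 1.5, 79.4% | 2, 87.8% |
| 20% | 3, 96.5% | 4, 98.8% |

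**The case against.** The strongest defence is that 7.4 means no more than stopping drug. The protocol uses removal language loosely. Section 10.1 itself lists, as a reason to stop therapy, "Adverse Events requiring removal from study (See Section 6.0". Section 5.2.2 removes patients for a single week, 6.1.1.1d pulls them and re-evaluates them at the next visit, and Table 5 takes them off therapy and later reintroduces them. On that reading 10.1 already calls for follow-up data, Week 8 falls well inside the 10-month window, and 12.4 does not make the 8-week MRI conditional on still taking drug.

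Much of this stands: the clash with 10.1 and 10.2 is an ambiguity, not a firm contradiction. But the loose wording in 10.1 is tied to adverse events under section 6, and the looser uses in 5.2.2, 6.1.1.1d and Table 5 come with a route back. Section 7.4 has neither feature. The defence also leaves open which data are required.

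A second objection is that the missing early-termination schedule affects every early stop, whether for hypotension, bronchospasm or refusal. That is correct. It is why rewording 7.4 alone would not secure a scan, and why the remedy must also sit in 10.1.

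A third is that a Week 8 scan after admission mixes infection, drug withdrawal and drug effect. Section 2.1 describes relapse after stopping, and 8.4 evaluates response at the highest tolerable dose. This also stands. It argues for identifying and separating such values, not for leaving them uncollected.

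A reader might also infer that 7.4 contradicts 11.5. It does not. Section 11.5 says who is analysed, and 7.4 excludes nobody from analysis. The patient remains in the response set with a missing value.

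**Conclusion.** The point holds as a minor one. Section 7.4 states a rule that differs from 7.1, is absent from the list in 10.2, and, if followed to the letter before Week 8, removes the only post-baseline MRI, QMR and body-water values from patients with a serious infection. Per patient lost, the cost is 5.0% to 6.7% of the planned sample and a rise of about 2.6% to 3.5% in the standard error of a mean change.

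A reader might go further and conclude that the trial's results are biased or that its primary endpoint is at risk. The documents do not support that. The size and direction of any bias rest on an admission rate and a difference d that are not given. Section 4.2.9 excludes uncontrolled active infection at entry and treatment lasts at most 8 weeks, so events may be few. Tolerability, the primary endpoint in 11.2.2, and adverse-event data are largely protected by 10.1, 12.1 and the reporting rules in 14.2.1. Aim 1.1.1 loses a little precision, with no bias shown.

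The conclusion assumes that site staff might apply 7.4 literally. If they treat it as stopping drug and bring the patient back at Week 8, nothing is lost.

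**What to change.** - **Section 7.4:** replace removal from the study with removal from protocol therapy.
- **Section 10.1, list of reasons:** add admission for IV antibiotics.
- **Section 10.1, follow-up:** state that patients off therapy for any reason who have not withdrawn consent complete the scheduled Week 8 questionnaires, examination, girth measurement, MRI and QMR, with body water where feasible and no biopsy.
- **Data and reporting:** record the date of last dose, so that off-drug Week 8 values can be identified and on-drug results shown separately. This is needed because the Abstract reports rebound of symptoms after stopping.

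The rules on when drug stops do not change. The cost is wording in two sections and one date to be recorded. No visit or procedure is added, because Week 8 is already in Table 6. The downside is a few off-drug assessments, some in recently ill patients, that need separate interpretation. Body water is the most demanding, since section 11.3.2 requires fasting, oral tracers and blood draws about 3 to 4 hours apart; hence the feasibility condition.

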## 8.0 EVALUATIONS/MATERIAL AND DATA TO BE ACCESSIONED

### 8.1 Required Clinical, Laboratory and Disease Evaluation

Baseline evaluations are to be conducted within 2 weeks prior to start of protocol therapy. Scans and x-rays must be done  $\leq 4$  weeks prior to the start of therapy. In the event that the patient's condition is deteriorating, laboratory evaluations should be repeated within 48 hours prior to initiation of the next dose escalation of propranolol.

**Table 6. Study schedule and evaluations**

STUDIES TO BE OBTAINED	Pre-Study	Wk 1	Wk 2	Wk 3	Wk 4	Wk 5	Wk 6	Wk 7	Wk 8
Informed consent	x								
Demographics	x								
Medical history	x								
Questionnaires	x	x	x		x		x		x
Physical exam	x	x	x		x		x		x
LM measurements	x	x	x		x		x		x
Vital signs	x	x	x		x		x		x
Height	x	x	x		x		x		x
Weight	x	x	x		x		x		x
CBC w/diff, platelets	x				x				x
Cr	x				x				x
Blood glucose	x	x a	x a		x a		x a		x a
EKG	x	x a	x a		x a		x a		x a
Echocardiogram a	x								
serum $\beta$ -HCG for females of childbearing potential	x								
Adverse event evaluation	x	x	x	x	x	x	x	x	x
Skin Biopsies	x								x
CXR a	x								
MRI	x								x
QMR	x								x
Body water content evaluation	x								x

aIf clinically indicated after initial evaluation

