## 2.0 BACKGROUND

	Primary Endpoint (Aim 1)	Secondary Endpoint (Aim 2)
Subjective Assessment	Questionnaires QOL	Questionnaires
	Short Form 36 Lymph-ICF Lymph-ICF-LL	Symptoms (Drainage, pain) Activity levels Clothing size change
Objective Assessment	Clinical and radiological Exam	Clinical and radiological Exam
	Blood pressure Heart rate Blood sugar Whole Body MRI QMR Deuterium and NaBr	Weight, BMI Limb girth discrepancy CTCAE Grading for Lymphedema Imaging: QMR, whole body MRI Blood and Tissues Circulation biomarkers IHC lymphatic vessel phenotype PIK3CA mutational analysis Next Gen sequencing analysis

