#### **2.3.2.3 Hypoglycemia:**

Propranolol has been reported to cause hypoglycemia in infants treated with propranolol. While these data is not established in old patients, all study patients will be encouraged to keep a regular food schedule and snack if they feel fatigued or dizzy.

If patients become ill for other reasons during the study period (eg URIs, gastroenteritis) during the study period, they are encouraged to contact us. Their propranolol dose will be held until they are able to tolerate POs.

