Below normal range, symptomatic	Discontinue propranolol (off protocol therapy. Re-evaluate after 2 weeks. If HR and BP then fall within normal parameters they will be reintroduced to the study with dose de-escalation to the prior tolerated dose of propranolol. If HR/BP below normative range at 0.5mg/kg/day, patient will be removed from study)

Hypoglycemia	Management/Next Dose for propranolol
Blood glucose >80 mg/dl	No change in dose
Blood glucose <80, >60, asymptomatic	Clinical evaluation, review feeding schedule, repeat test after more

Hypoglycemia	Management/Next Dose for propranolol
	frequent/supplemental feeds
Blood glucose <80, symptomatic	Discontinue propranolol (off protocol therapy)

Bronchospasm	Management/Next Dose for propranolol
Transient/self-limited episode	Clinical evaluation, may continue at same dose
Associated with URI	Hold propranolol till URI resolves; if >7 days, off protocol
Not associated with URI, persistent or requiring new medical treatment	Discontinue propranolol (off protocol therapy)

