## 8.4 Statistical Analysis

Descriptive statistics will be used to summarize patient characteristics, toxicity data, response data and biomarker expression. Toxicity rates at each dose tested will be presented with 95% exact confidence intervals. Responses will be evaluated among patients treated at the highest tolerable dose. Continuous outcomes will be summarized using mean  $\pm$  standard deviation or median (interquartile range) for non-normal data. Comparisons between groups and response changes from baseline will be evaluated using two-sided t-tests or the non-parametric equivalent Wilcoxon Rank-Sum test (for non-normal data). Association between PIK3CA mutational status and patient response will be assessed using chi-square/Fisher exact test. All analyses will be performed using a type I error of 0.05. Biostatistics will be done using Irving Institute for Clinical and Translational Research statistical services at Columbia University Medical Center.

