## 11.2 Study Design/ Endpoints (Table 2)

11.2.1 **Study design:** Each patient will serve as his/her own control, for comparison of study questionnaires (subjective) and with changes in the clinical measurements and imaging measurements of the anatomic area affected by lymphatic malformation compared before and after treatment (objective). In our experience, children exhibiting responses to propranolol displayed these within 2 weeks of beginning propranolol treatment, with estimated reduction in the overall volume of the affected area exceeding 20%.

11.2.2 **Primary endpoints:** The primary endpoint will be the tolerability of escalating dosage of propranolol both by subjective reporting (survey instrument) as well as objective measurements of vital signs. Survey instruments include a general quality of life (QOL) and function survey (SF-36), as well as validated survey instruments for patients with lymphedema (LYMPH—ICF, LYMPH—LCF—LL)[38, 39].

11.2.3 **Secondary endpoints:** The secondary endpoints of the study will be both subjective and objective evaluation of the lymphedema after propranolol treatment, as measured by both survey instrument and objective measurements (clinical exam and radiological studies), as well as biological assays from tissues obtained from biopsies.

11.2.3.1 We will determine whether higher doses of propranolol are well tolerated in this patient population. Secondarily, we will measure determine whether higher doses correlate with improvement in lymphedema symptoms and signs, and healing or improvement of skin lesions, if present (reduced lymphatic leakage, reduced bleeding). Skin lesions will be photographed at clinical visits, and daily lymphatic fluid losses estimated by weight measurements.

Using MRI and body composition analysis, we will determine whether propranolol decreases lymphedema, alters edema water content and location (intracellular vs. interstitial), or alters adiposity of affected extremity.

We will study the biologic activity of oral propranolol against lymphedema, by examining the expression of progenitor cell markers, lymphatic endothelial cell markers, beta-adrenergic receptor expression, macrophage markers and detection of adipocyte content of biopsy specimens (see table below). Results will be compared to ultrasound and magnetic imaging data.

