### **12.0 EVALUATION CRITERIA**

#### 12.1 **Adverse Events**

Any patient who receives the study drug will be evaluable for Adverse Effects. This study will utilize the NIH Common Terminology Criteria for Adverse Events v4.0 (CTCAE) for evaluating adverse events.

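### On-treatment glucose is tested only when clinically indicated, so the plan cannot estimate a rate of low glucose, and the documents disagree on whether blood sugar is a primary measure

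*Combined protocol and SAP*

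**What the plan says.** **Endpoint status.** Table 2, in the objective part of the primary-endpoint column, reads "Blood pressure Heart rate Blood sugar Whole Body MRI QMR Deuterium and NaBr". Two other statements of the endpoint leave glucose out. Aim 1.1.2b limits objective tolerability to heart rate and blood pressure, and Section 11.2.2 refers to "objective measurements of vital signs" alongside the surveys.

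**Measurement.** In Table 6, blood glucose is unconditional at the pre-study visit only. The entries at Weeks 1, 2, 4, 6 and 8 all carry footnote a: "If clinically indicated after initial evaluation". Vital signs have no such footnote at any visit. Table 5 nevertheless has a dosing-guideline row for "Blood glucose <80, >60, asymptomatic". Section 2.3.2.3 tells patients to "snack if they feel fatigued or dizzy" and does not ask for a glucose test at that point.

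**Analysis.** Section 8.4 states: "Toxicity rates at each dose tested will be presented with 95% exact confidence intervals". Section 12.1 states: "Any patient who receives the study drug will be evaluable for Adverse Effects". Neither section says how a patient with no on-treatment glucose value is handled.

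**The concern.** A rate needs a numerator and a denominator drawn from the same patients. Here the numerator can come only from patients someone decided to test, while the nearest statement on the denominator covers everyone treated. A patient with low glucose and no symptoms has no planned route into the numerator.

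This matters whether or not blood sugar stays a primary measure. The abstract defines tolerability partly by known propranolol adverse effects and names hypoglycemia among them, and Table 7 lists it as a known toxicity. Section 2.3.2.3 says the evidence comes from infants and is not established in older patients. This trial enrolls patients aged 12 and over, so its own data are what a reader would look to. A low reported rate could then reflect little testing rather than little hypoglycemia, and the report would not show which.

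**Working it through.** The documents give no expected hypoglycemia rate for this trial and no precision target, so there is no planned figure to reproduce. The inputs are the planned enrollment of 15–20 (Section 11.1), the exact 95% interval (Section 8.4), the Table 6 schedule, and the dose schedule in Table 1 and Section 5.1. The true rate and the share tested are assumptions.

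**1. Does another section close the gap?** Section 8.1 asks for repeat laboratory tests only when a patient is deteriorating. Table 6 schedules an adverse event evaluation every week, which can pick up symptoms but not a low value without symptoms. The gap stays open.

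**2. All treated patients as denominator.** Let p be the true rate and s the share of affected patients who are tested. The expected reported rate is p × s, and the chance of seeing at least one case in n patients is 1 − (1 − p × s)^n. With p = 10% and n = 20:

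| s (assumed) | Expected reported rate | Chance of at least one case |
|---|---|---|
| 100% | 10% | 87.8% |
| 50% | 5% | 64.2% |
| 25% | 2.5% | 39.7% |
| 10% | 1% | 18.2% |

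The rate is biased low whenever s is below 100%. For asymptomatic cases tested without regard to glucose, s equals the overall fraction tested. For all hypoglycemia it does not, because indicated testing picks out likely cases.

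**3. Tested patients only as denominator.** Let s1 be the share tested among patients with low glucose and s0 the share among the rest. The expected rate is about p × s1 / (p × s1 + (1 − p) × s0). It equals p when s1 = s0 and exceeds p when s1 > s0. With p = 10%, s1 = 50% and s0 = 10% (assumed): 0.05 / (0.05 + 0.09) = 0.357, or about 36%. On the same assumptions, the all-treated denominator gives 0.10 × 0.50 = 5%. The reported figure would be about 5% or about 36% against a true 10%, depending on a choice the plan does not make.

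**4. The interval.** For zero events the exact 95% upper limit is 1 − 0.025^(1/n):

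- n = 20: 1 − 0.025^(1/20) = 16.8%
- n = 15: 1 − 0.025^(1/15) = 21.8%

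These limits hold only if all n patients were tested. The harm to coverage is not uniform. With all 20 treated patients as denominator and a true rate of 20%, coverage of the nominal 95% interval falls from 97.8% (s = 100%) to 87.8%, 64.2% and 33.2% (s = 50%, 25% and 10%). With a true rate of 10% it does not fall, because even zero events in 20 leaves 10% inside the interval.

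**5. Which doses can existing draws cover?** Table 6 already takes blood from every patient at Weeks 4 and 8 for CBC and creatinine. Under Table 1 and Section 5.1 a patient arrives at Week 4 on 1 mg/kg/day and at Week 8 on 3 mg/kg/day. The 0.5 and 2 mg/kg/day levels are in effect on arrival at Weeks 2 and 6, when no universal draw is planned. (Section 5.2.2 gives a different starting dose in its opening sentence; that must be reconciled, and the mapping here follows Table 1.)

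**The case against.** **Primary status is contested.** Only Table 2 lists blood sugar. On Aim 1.1.2b and Section 11.2.2, glucose is a safety laboratory test, and testing it on indication is a defensible choice. This stands as far as it goes: the first defect is an inconsistency between sections. It does not rescue the rate, because Section 8.4 covers toxicities generally.

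**A reader might infer that untested patients will be scored as free of hypoglycemia.** The documents do not say so. Section 12.1 defines who is evaluable for adverse effects; it does not score a missing glucose as normal. The denominator, and with it the direction of bias, is left undefined.

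**A reader might take 0 of the patients tested as the honest limit.** If 4 of 20 were tested and none was low, the 0/4 upper limit is 60.2%. That does not describe the dose cohort either, because four patients tested for symptoms are not a random sample. Nor does an example with 20 patients fit 3 mg/kg/day, since patients who do not tolerate escalation never reach that dose.

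**Symptomatic events have a route to detection.** Weekly adverse event evaluation applies to everyone, so the gap falls mainly on asymptomatic values. This stands, with the qualification that the advice to snack when tired or dizzy may leave some symptomatic episodes unmeasured. Also, the asymptomatic row in Table 5 guides dosing; no section says such a value counts as a toxicity under Section 8.4.

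**Full testing adds little power.** At the 0.9% in Table 7, testing all 20 patients finds at least one case with probability 1 − (1 − 0.009)^20 = 16.5%. The gain is a valid interval, not a good chance of detection.

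**Conclusion.** The concern holds in limited form. The plan promises toxicity rates by dose, but on-treatment glucose is not measured systematically, so no valid rate of low glucose on treatment can be estimated under either denominator. Counting all treated patients biases the rate low; counting only tested patients probably biases it high. The size cannot be stated from the documents, because it depends on the share tested, and every percentage above that uses such a share is illustrative. The firm figure is that 16.8% (0 of 20) or 21.8% (0 of 15) is a valid upper limit only with complete testing.

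A reader might go further and conclude that the trial will report a falsely reassuring rate at its highest dose. The documents do not support that as fact: it needs an all-treated denominator and a low share tested, neither of which is written. What is established is that Table 2, Aim 1.1.2b, Section 11.2.2 and Table 6 do not agree, and that Section 8.4 has no rule for patients without a glucose value.

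**What to change.** 1. Reconcile Table 2, Aim 1.1.2b and Section 11.2.2 on whether blood sugar is a primary measure.
2. In Table 6, remove footnote a from blood glucose at Weeks 4 and 8. Run it in every patient on the blood already drawn for CBC and creatinine, before any escalation that day. Record time since last meal, time since last dose, and the dose the patient was on at the draw. Meal timing matters because the body-water test scheduled at Week 8 uses a fasting draw (Section 11.3.2).
3. In Section 8.4, define low glucose in advance and report number low over number tested, with an exact interval, only for the doses sampled at those draws. Under the planned schedule these are 1 and 3 mg/kg/day, plus any lower dose at which a patient was actually held. Make no rate claim for doses without universal testing.
4. Report glucose taken for symptoms separately, as clinically detected hypoglycemia, with the number tested at each dose.
5. Reconcile the rows of Table 5, which do not cover a value of exactly 80 mg/dl or an asymptomatic value of 60 or below.

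The cost is one extra assay on two existing draws, or 30–40 assays for 15–20 patients (2 × 15 to 2 × 20), plus a few lines in Section 8.4. No visit or procedure is added. The reported rate may look less favorable. If the sponsor prefers not to add the assay, the consistent alternative is to take blood sugar out of the primary measures and report only clinically detected hypoglycemia, labeled as such.
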